##### 4.2 INCLUSION CRITERIA

1. Patients able to provide written informed consent for participation in this trial.
2. Males or females, 18 to 75 years of age, both inclusive.
3. Female must be either of non-child bearing potential (surgically sterilized at least 6 months prior to screening or postmenopausal) or using one or more methods of contraception.
4. Histologic confirmation of NASH without cirrhosis (fibrosis stage 0, 1, 2, or 3) from liver biopsy performed either during the screening period or no more than 6 months prior to the first visit, with a NAS of  $\geq 4$  and a score of at least 1 in each (steatosis scored 0-3, ballooning scored 0-2 and lobular inflammation scored 0-3). If biopsy was performed within 6 months of screening, the slides, biopsy material or block should be available for baseline documentation. Such patients, whose historical biopsy report is available, should not use medications suspected of having an effect on NASH for at least 3 months prior to the screening.
5. BMI  $\geq 25$  kg/m^2.

	Approved by: [name] [name]	Protocol No.: SARO.17.004.02.PROTOCOL Version No.: 2.0
---	---	---

 Zydus Discovery DMCC	CLINICAL TRIAL PROTOCOL Saroglitazar Magnesium – Phase 2 SARO.17.004	CONFIDENTIAL Page 28 of 76
--	---	---

6. For hypertensive patients, blood pressure must be controlled by a stable dose of antihypertensive medications for at least 3 months prior to screening (and the stable dose can be maintained throughout the study)
7. Patients with type 2 diabetes mellitus may be included if they fulfil the following criteria;
  - a. Stable therapeutic regimen as defined by no changes in oral agents or dose for at least 3 months before screening and the stable dose can be maintained throughout the study.
  - b. HbA1c  $\leq$  9.5%.
8. Patients agree to comply with the study procedure.

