#### 4.3 EXCLUSION CRITERIA

1. Pregnant and lactating female.
2. Positive pregnancy test.
3. Patients with history of myopathies or evidence of active muscle diseases.
4. Patients with history of alcohol consumption of  $>30$  gm/day for men,  $>20$  gm/day for women for consecutive previous 2 years and/or drug abuse.
5. Known allergy, sensitivity or intolerance to the study drug or formulation ingredients.
6. Participation in an interventional clinical study and/or receipt of any investigational medication within 3 months prior to screening.
7. History of malignancy in the past 5 years and/or active neoplasm with the exception of superficial, non-melanoma, skin cancer.
8. Any of the following laboratory values at screening:
  - a. Direct bilirubin  $>1.5$  mg/dL
  - b. Serum albumin  $<2.5$  g/dL
  - c. Estimated glomerular filtration rate (eGFR)  $<60$  mL/min/1.73m^2
  - d. Serum alanine aminotransferase (ALT) or aspartate aminotransferase (AST)  $>200$  IU/L
  - e. Patients with international normalized ratio (INR)  $>1.5$
  - f. Creatinine kinase  $\geq 1.5$  ULN

	Approved by: [name] [name]	Protocol No.: SARO.17.004.02.PROTOCOL Version No.: 2.0
--	------------------------------------	---

 Zydus Discovery DMCC	CLINICAL TRIAL PROTOCOL Saroglitazar Magnesium – Phase 2 SARO.17.004	CONFIDENTIAL Page 29 of 76
--	---	---

- g. Lipase  $\geq$ ULN
  - h. Amylase  $\geq$  ULN.
9. Unstable cardiovascular disease, including:
- a. unstable angina, (i.e., new or worsening symptoms of coronary heart disease within the 3 months preceding screening), acute coronary syndrome within the 6 months preceding Screening, acute myocardial infarction within the 3 months preceding screening or heart failure of New York Heart Association class (III – IV) or worsening congestive heart failure, or coronary artery intervention, within the 6 months preceding screening
  - b. history of (within 3 months preceding Screening) or current unstable cardiac dysrhythmias
  - c. uncontrolled hypertension (systolic blood pressure [BP] > 155 mmHg and/or diastolic BP > 95 mmHg)
  - d. Stroke or transient ischemic attack within the 6 months preceding screening.
10. Previous history of bladder disease and/or hematuria.
11. Previous liver biopsy that demonstrated presence of cirrhosis or radiologic imaging consistent with cirrhosis or portal hypertension.
12. Type 1 diabetes mellitus.

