### 5.8.2 Restricted Concomitant Medications

Drugs affecting insulin resistance (Glitazones/Glitazars/GLP-1 agonists) will not be allowed during the study.

Other drugs claimed for treatment of NASH (pentoxifyllin, ursodeoxycholic acid, antioxidants such as vitamin E (>800 IU/day), glutathione, orlistat, betaine, incretin mimetics or non-prescribed complementary alternative medications (including dietary supplements, megadose vitamins, herbal preparations and special teas) will not be allowed during the study. *However, patients who are taking stable dose of Vitamin E for at least 3 months will be enrolled in the study.*

Subjects also should not take any non-allowed over-the-counter medications or complementary and/or alternative medications believed to have a potential impact that would affect the ability to evaluate the study data.

	Approved by: [name] [name]	Protocol No.: SARO.17.004.02.PROTOCOL Version No.: 2.0
---	------------------------------------	---

 Zydus Discovery DMCC	CLINICAL TRIAL PROTOCOL Saroglitazar Magnesium – Phase 2 SARO.17.004	CONFIDENTIAL Page 39 of 76
---	---	---

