### 5.8.3 Permitted Concomitant Medications

With the exception of excluded concomitant medications, other medications that subjects have been taking at stable dosages for at least 3 months prior to biopsy, i.e., statins, drugs for glycemic control and hypertension will be permitted as concomitant medications. To the extent possible, subjects should continue with their current regimen of medication without any change throughout the study.

[figure not shown]
Allowed over-the-counter medications include acetaminophen (maximum 1 gram/day), ibuprofen (maximum 800 mg/day) or naproxen (maximum 440 mg/day) or antacids such as H2 receptor blockers or proton-pump inhibitors for shorter duration as per Investigator discretion.

The PI should be alerted if, during the course of the study, a subject requires a new medicine or therapy or a change to an established dosing regimen. All medications that target NAFLD or NASH, or have been suggested to target the underlying causes of NAFLD or NASH, should be reviewed and agreed on by the PI, Medical Expert and Sponsor before being taken by the subject.

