### 6.2.3 Blood Samples

Multiple venipunctures should be avoided to collect blood samples. It is recommended to collect blood sample for safety and efficacy measurement at a given visit.

Samples for secondary and exploratory efficacy variables will be assessed as follows:

[figure not shown]
- Liver function tests include ALT, AST, ALP, direct bilirubin, GGT, total proteins and albumin.
- Lipid parameters and lipoproteins include LDL, sdLDL, VLDL, HDL, triglyceride, total cholesterol, non HDL cholesterol, and Apolipoprotein A1, Apolipoprotein B.
- Glycemic control includes FPG, fasting insulin, adiponectin, C-peptide, HOMA IR, HOMA beta and HbA1c.

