6.4 Statistical Methods for Efficacy Analyses

This is a proof of concept study with a small number of patients enrolled. All primary and secondary efficacy endpoints will be summarized descriptively by treatment as per section 6.1 for both mITT and PP populations.

Fisher's exact test will be used to compare the treatment differences for following endpoints in Saroglitazar 2 mg and Saroglitazar 4 mg treatment groups with placebo.

Document Title:	Statistical Analysis Plan		
Version Number:	1.0	Date:	31 Mar 2020
Protocol Number:	SARO.17.004	Sponsor Name:	Zydus Discovery DMCC

- Percentage of patients with decrease from baseline in NAFLD activity score by at least 2 point spread across in at least 2 of the NAS components (steatosis, hepatocyte ballooning, and lobular inflammation) at Week 24 with no worsening of fibrosis.
- Percentage of patients with disappearance of steatohepatitis at Week 24.

Disappearance of steatohepatitis is defined as:

- resolution of steatohepatitis on overall histopathological reading and no worsening of liver fibrosis on NASH CRN fibrosis score (or)
- improvement in liver fibrosis greater than or equal to one stage (NASH CRN fibrosis score) and no worsening of steatohepatitis (defined as no increase in NAS for ballooning, inflammation, or steatosis).

Resolution of steatohepatitis is defined as absent fatty liver disease or isolated or simple steatosis without steatohepatitis and a NAS score of 0–1 for inflammation, 0 for ballooning, and any value for Steatosis.

Two-sample t-test will be used to compare the treatment differences for the following endpoints in Saroglitazar 2 mg and Saroglitazar 4 mg treatment groups with placebo.

- Change from baseline in stage of steatosis, lobular inflammation and ballooning at Week 24.
- Change from baseline in stage of fibrosis at Week 24.
- Change from baseline in liver function tests parameters (ALT, AST, ALP, GGT, Direct bilirubin, Total proteins and Albumin) at Week 24.
- Change from baseline in lipid profile parameters (TG, TC, sdLDL, HDL, LDL, VLDL, non-HDL, ApoA1 and ApoB) at Week 24.
- Changes from baseline in glycemic control and insulin resistance parameters (FPG, HbA1c, Fasting insulin, C-peptide, Adiponectin, HOMA-B and HOMA-IR) at Week 24.

In addition to the descriptive summaries, treatment differences and 95% confidence for the treatment differences will be provided. All p-values presented are for the descriptive purpose only.

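### Insulin-treated type 2 diabetics are not excluded, yet fasting insulin, HOMA-IR and HOMA-B are analysed in every patient with no rule for insulin users

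*SAP*

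**What the plan says.** **Who can enrol.** Protocol 4.2, criterion 7, opens with "Patients with type 2 diabetes mellitus may be included if they fulfil the following criteria". The criteria are an HbA1c of at most 9.5% and a stable regimen, described as "Stable therapeutic regimen as defined by no changes in oral agents or dose for at least 3 months before screening", with that dose to be maintainable through the study. The only type of diabetes excluded in Protocol 4.3 is "Type 1 diabetes mellitus".

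**Which drugs are allowed.** Protocol 5.8.2 states "Drugs affecting insulin resistance (Glitazones/Glitazars/GLP-1 agonists) will not be allowed during the study" and also bars incretin mimetics; insulin is not on the list. Protocol 5.8.3 says that, at stable dosages for at least 3 months before biopsy, "statins, drugs for glycemic control and hypertension will be permitted as concomitant medications". It asks patients to stay on their current regimen as far as possible, and provides for the investigator to be told of changes.

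**What is analysed.** Protocol 6.2.3 states "Glycemic control includes FPG, fasting insulin, adiponectin, C-peptide, HOMA IR, HOMA beta and HbA1c". SAP 6.4 lists the same seven parameters for two-sample t-tests of each dose against placebo: "Changes from baseline in glycemic control and insulin resistance parameters (FPG, HbA1c, Fasting insulin, C-peptide, Adiponectin, HOMA-B and HOMA-IR) at Week 24". On the population it says "All primary and secondary efficacy endpoints will be summarized descriptively by treatment as per section 6.1 for both mITT and PP populations", and SAP 3.1 makes mITT primary for all efficacy analyses. SAP 6.6 plans no subgroup analysis. Neither document has a rule for patients on insulin, and the SAP gives no HOMA formula.

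**The concern.** HOMA-IR and HOMA-B are calculated from fasting glucose and fasting insulin, on the premise that the insulin measured is the patient's own. In a patient who injects insulin, the measured value can depend on dose, time since injection and whether the assay picks up the injected product. The three insulin-based variables would then be hard to read as insulin resistance or beta-cell function.

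Change in insulin resistance is a stated secondary objective (Protocol 3.2, SAP 2.1). In a descriptive study the arm means, differences and confidence intervals are the result, and with 6, 6 and 3 patients one unusual change can dominate them. If the handling is settled only after unblinding, the choice may look driven by the data.

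**Working it through.** **1. Can an insulin user enter?** Side by side, Protocol 4.2 admits type 2 diabetics, 4.3 removes only type 1, 5.8.2 does not name insulin, and 5.8.3 permits drugs for glycemic control as a class. A patient on stable insulin is therefore not excluded. This is an inference from silence plus a general permission. No section names insulin as a treatment, and criterion 7a speaks of oral agents.

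**2. Does another part of the plan catch it?**
- The PP analysis (Protocol 8.2.1.3, SAP 6.5) removes patients with relevant protocol deviations. A permitted drug is not a deviation, so an insulin user stays in.
- Protocol 7.1 requires an overnight fast and 5.2 regulates study-drug timing before the blood draw. Neither addresses the timing of an insulin injection.
- Protocol 5.8.1 records all concomitant drugs and dose changes from 30 days before Visit 1, and SAP section 5 lists them. Insulin users can be identified, but nothing is done with that information.

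**3. How many parameters are exposed?** Seven are listed. Fasting insulin, HOMA-IR and HOMA-B use measured insulin (3 of 7). FPG, HbA1c, C-peptide and adiponectin do not (4 of 7). Under the usual HOMA formulas (an assumption, since the SAP gives none), both indices are proportional to insulin at fixed glucose: a change in measured insulin by a factor of 1.5, 2 or 3 changes each index by the same factor.

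**4. Arm sizes.** The plan's split of 15 by 2:2:1 reproduces: 15 × 2/5 = 6, 15 × 2/5 = 6, 15 × 1/5 = 3.

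**5. Chance that at least one insulin user enrols.** The documents give no share p, so a range is assumed. The formula is 1 − (1 − p)^n.

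| Assumed share p | At least one of 15 | At least one in an arm of 6 | At least one in placebo (3) |
|---|---|---|---|
| 5% | 53.7% | 26.5% | 14.3% |
| 10% | 79.4% | 46.9% | 27.1% |
| 20% | 96.5% | 73.8% | 48.8% |
| 30% | 99.5% | 88.2% | 65.7% |

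**6. Leverage of one patient.** If one patient's change is displaced by k SD (the SD among the other patients), the arm mean moves by k/n.
- k = 1: 0.33 SD in placebo, 0.17 SD in an active arm.
- k = 2: 0.67 and 0.33 SD.
- k = 5: 1.67 and 0.83 SD.

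For comparison, the 95% CI half-width for 6 against 3 is t(0.975; 7 df) × √(1/6 + 1/3) = 2.365 × 0.707 = 1.67 SD. A 5 SD displacement of one placebo patient moves that mean by as much as the whole half-width. It would also inflate the SD.

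**7. Price of leaving a patient out.** If one placebo patient is removed, the half-width for 6 against 2 is t(0.975; 6 df) × √(1/6 + 1/2) = 2.447 × 0.816 = 2.00 SD. If two are removed, one remains and no placebo SD can be computed.

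**The case against.** The plan aims at constant background treatment: criterion 7a and Protocol 5.8.3 both ask for stable regimens. At a constant insulin dose, part of any distortion is common to baseline and Week 24 and cancels in the change score. This stands and limits the concern mainly to patients whose dose or injection timing changes. It does not remove it: 5.8.3 asks for stability only as far as possible, and the explicit definition in 7a refers to oral agents.

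Four of the seven parameters are unaffected, the median, minimum and maximum would show an outlier, there is no formal hypothesis test, and p-values are descriptive. All this stands and keeps the point small.

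A reader might infer more than the documents support:
- **That insulin-treated patients are expressly eligible.** They are only not excluded. The mention of oral agents may mean that orally treated diabetics were intended.
- **That the insulin-resistance objective does measure injected insulin.** That needs such a patient to enrol and an assay that detects the injected product. The documents state neither.
- **That a fall in HOMA-IR after an insulin dose cut is a false signal.** If glucose holds on less insulin, true sensitivity may have improved. A worked example would rest on invented glucose and insulin values, so none is given here.

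It is also tempting to drop anyone who used insulin at any time on study. Insulin use after randomisation may itself respond to treatment, so excluding on it would damage the randomised comparison.

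**Conclusion.** The point holds in a limited, conditional form. The protocol does not exclude insulin-treated type 2 diabetics, and the SAP analyses fasting insulin, HOMA-IR and HOMA-B in all mITT and PP patients with no rule for them. If one enrols and the assay detects injected insulin, three of the seven parameters in one secondary endpoint group may be partly uninterpretable. One patient with an insulin dose change could then dominate an arm mean, at a weight of 1/3 in placebo or 1/6 in an active arm.

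The primary endpoint, the histology endpoints and the other four glycaemic parameters are not affected. No figure in the plan is contradicted. The size of any actual distortion cannot be stated, because the share of users, the assay and the HOMA formula are not given; the percentages in the table rest wholly on assumed shares. This is a cheap improvement to the SAP.

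**What to change.** In SAP 6.4:
- Base the main summaries and treatment comparisons of fasting insulin, HOMA-IR and HOMA-B on patients with no exogenous insulin at baseline, identified from the concomitant-medication record, and show n per arm.
- Show the all-mITT summary of the same three variables beside it.
- Do not exclude patients for insulin started or changed after randomisation; flag them in the listing.
- Keep C-peptide, FPG, HbA1c and adiponectin in all patients. C-peptide is already collected and is the natural measure of the patient's own secretion in insulin users.

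This takes a short SAP text and one programming flag, with no new data. If no insulin user enrolled, nothing changes. Otherwise the cost is a smaller n for three variables, which matters most in placebo: two remaining patients give the wider interval worked out above, and one gives no SD. The all-mITT display is therefore needed as well.

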6.5 Sensitivity Analysis

A sensitivity analysis to explore the robustness of the efficacy results with respect to the protocol deviations will be performed using Per-Protocol population for the primary and secondary efficacy endpoints.

Statistical Analysis Plan			
Version Number:	1.0	Date:	31 Mar 2020
Protocol Number:	SARO.17.004	Sponsor Name:	Zydus Discovery DMCC

6.6 Subgroup Analyses and Effect of Baseline Factors

Due to the small sample size, no subgroup analysis is planned for this study.

6.7 Multiplicity Strategy

Not applicable.

6.8 Handling of Missing Data

Clarifications, wherever possible, will be obtained from the respective investigator for any missing data or for any illegible entry, unused or unauthenticated data. Subjects are required to have at least one post-baseline visit to be included in the mITT population. Last Observation Carried Forward (LOCF) will be used for the imputation of post-baseline missing values. Baseline values will not be carried forward for the imputation of missing values. Patients discontinued from study will be excluded from the PP population.

7. SAFETY ANALYSIS STRATEGY

Safety analyses will be conducted using the safety population on a treatment-emergent basis.

7.1 Safety Endpoints

The safety endpoints are:

- Frequency and Severity of Adverse events.
- Vital Signs (Systolic BP, diastolic BP, pulse rate, oral temperature and respiratory rate)
- Clinical laboratory testing (hematology, clinical chemistry and urinalysis)
- Twelve-lead electrocardiogram (ECG)
- Physical Examination.
- Body weight

7.2 Safety Hypothesis

There are no formal safety hypotheses in this study. The focus of the safety analysis will be a comprehensive descriptive assessment of the safety endpoints listed in Section 7.1.

Document Title:	Statistical Analysis Plan		
Version Number:	1.0	Date:	31 Mar 2020
Protocol Number:	SARO.17.004	Sponsor Name:	Zydus Discovery DMCC

7.3 Statistical Methods for Safety Analysis

Unless otherwise stated, the analysis population for all safety analysis is the safety analysis population as defined in Section 3.2.

7.3.1 Extent of Exposure

Study duration is defined as the date of last visit minus date of informed consent date plus one. Treatment duration is defined as the date of last dose minus the date of the first dose plus one. If the date of last dose is not available, the date of the last visit will be used in the calculation. If the date of first dose is not available, the date of baseline visit will be used in the calculation. Study duration and the treatment duration will be summarized descriptively.

Treatment compliance is calculated as the total number of tablets taken divided by the expected number of tablets to be taken during the study period multiplied by 100. Treatment compliance will be summarized descriptively. In addition, a categorical summary of compliance will also be presented using the following categories: < 80% 80% to 120% and >120%. A subject's is considered to be compliant, if he/she takes 80% to 120% of the study drug during the study period.

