If the patient has consumed restricted medications but is otherwise considered eligible to be enrolled into this study by the PI, a minimum of 1 month wash out period would be instituted before the screening visit.

Liver biopsy will be performed to confirm the diagnosis of NASH and record a baseline NAFLD Activity Score (Appendix 2). The histological evidence of NASH is defined as NAS  $\geq$  4 with a minimum score of 1 for all of its three components [steatosis, hepatocyte ballooning, and lobular inflammation].

Following confirmation of inclusion/exclusion criteria and upon histological confirmation of NASH by liver biopsy, patients will be enrolled into the study.

Eligible patients will be randomly assigned to receive Saroglitazar Magnesium 2 mg or 4 mg or placebo in a 2:2:1 ratio for 24 weeks.

Upon completion of 24 weeks of treatment, liver biopsy will be performed and the NAFLD Activity Score recorded (Appendix 2).

The scheduled visits during this study will be as follows:

- Visit 1: Screening Visit [-4 Week (-28 Days)],
- Visit 2: Enrollment Visit (Day 1  $\pm$  7 Days/Week 0),
- Visit 3: Day 43/Week 6  $\pm$  7 Days,
- Visit 4: Day 85/Week 12  $\pm$  7 Days,
- Visit 5: Day 127/Week 18  $\pm$  7 Days,
- Visit 6: Day 169/Week 24  $\pm$  7 Days,
- Visit 7: Follow-up Visit: Day 197/Week 28  $\pm$  7 Days,

Patients will be advised to follow a stable lifestyle. No change in the intensity of lifestyle (Diet/Exercise) will be allowed during the period of study. Patients will be monitored for safety and efficacy parameters as per Table No 1.

If further investigations are required in case of any AE, Investigator is advised to assess the AE and take necessary action, if required. Patients are advised to contact the Investigator for any complaints.

	Approved by: [name] [name]	Protocol No.: SARO.17.004.02.PROTOCOL Version No.: 2.0
---	---	---

 Zydus Discovery DMCC	CLINICAL TRIAL PROTOCOL Saroglitazar Magnesium – Phase 2 SARO.17.004	CONFIDENTIAL Page 48 of 76
---	---	---

[figure not shown]

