2.2.1 Study design

This is a Phase 2 randomized, multi-center, double-blind, placebo-controlled proof of concept study to evaluate the safety and efficacy of Saroglitazar magnesium 2 mg and 4 mg in patients with NASH meeting pre-specified inclusion/ exclusion criteria. Male and female patients aged 18 to 75 years will be enrolled in this study. Approximately 15 patients who meet the inclusion and exclusion criteria will be enrolled.

Liver biopsy will be performed at the screening visit to confirm the diagnosis of NASH and to record the baseline NAFLD Activity Score. The histological evidence of NASH is defined as $NAS \geq 4$ with a minimum score of 1 for all of its three components [steatosis, hepatocyte ballooning and lobular inflammation].

This study will be conducted over a period of up to 32 weeks and will include a 4-week screening phase, a 24-week treatment phase and a safety follow-up visit, 4 weeks after the last treatment. The study plan is provided below.

Document Title:	Statistical Analysis Plan		
Version Number:	1.0	Date:	31 Mar 2020
Protocol Number:	SARO.17.004	Sponsor Name:	Zydus Discovery DMCC

[figure not shown]
NOTE: Liver biopsy showing NASH within 6 months preceding Visit 1 can be used.

The study visits are planned at screening [-4 Week (-28 days)], Baseline/Enrollment Visit (Day 1 ± 7 days), Week 6 (Day 43 ± 7 days), Week 12 (Day 85 ± 7 days), Week 18 (Day 127 ± 7 days), Week 24 (Day 169/ ± 7 days) and a safety follow-up visit at Week 28 (Day 197 ± 7 days). All patients will be advised to follow a stable lifestyle. No change in the intensity of lifestyle (Diet/Exercise) will be allowed during the study period.

Document Title:	Statistical Analysis Plan		
Version Number:	1.0	Date:	31 Mar 2020
Protocol Number:	SARO.17.004	Sponsor Name:	Zydus Discovery DMCC

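### The fallback for a missing last-dose date has no cap at end of treatment, so the off-drug Week 28 visit can be counted as exposure (about 28 to 29 days too long for a completer)

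*SAP*

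**What the plan says.** SAP 7.3.1 (Extent of Exposure) defines two durations. For the study as a whole: "Study duration is defined as the date of last visit minus date of informed consent date plus one". For drug exposure: "Treatment duration is defined as the date of last dose minus the date of the first dose plus one". Both are to be summarised descriptively.

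Two fallbacks follow. A missing first-dose date is replaced by the baseline visit date. For the other end of the interval the rule is: "If the date of last dose is not available, the date of the last visit will be used in the calculation".

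On the calendar, SAP 2.2.1 describes "a 24-week treatment phase and a safety follow-up visit, 4 weeks after the last treatment". Protocol 7.1 puts the Week 24 visit (Visit 6) at Day 169 and lists "Visit 7: Follow-up Visit: Day 197/Week 28", each with a window of 7 days either side. In Protocol 7.2, drug is last dispensed at Visit 5 and medication compliance is last assessed at Visit 6. Visit 7 has neither; only concomitant medication is reviewed.

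**The concern.** The fallback uses the same term, the date of the last visit, that the same paragraph uses to close study duration. Read consistently, it means the visit at which the patient leaves the study. For a completer that is Visit 7, which by design falls about four weeks after dosing ends. The rule then counts the drug-free follow-up as treatment. The first-dose fallback does not share this problem, because dosing starts at the baseline visit.

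What is at stake is the exposure table. With 15 patients and no formal hypothesis testing, description is the trial's output, and a single record visibly moves an arm mean. A tabulated duration of 197 days would also be at odds with a planned 24-week treatment period.

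**Working it through.** **Inputs.** Treatment of 24 weeks (SAP 2.2.1; Protocol 5.2). Visit 6 at Day 169 and Visit 7 at Day 197, each ±7 days (Protocol 7.1). Arm sizes 6, 6 and 3 (SAP 4). First dose assumed on Day 1.

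**The plan's own calendar.** Screening, treatment and follow-up give 4 + 24 + 4 = 32 weeks, which matches the stated total. The visit days also reproduce: 24 × 7 + 1 = 169 and 28 × 7 + 1 = 197.

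**Completer, last-dose date missing.** Duration = last dose − first dose + 1.

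| Actual last dose | Actual duration | Duration under the rule | Excess |
|---|---|---|---|
| Day 168 (day before Visit 6) | 168 − 1 + 1 = 168 | 197 − 1 + 1 = 197 | 29 days; 29/168 = 17.3% |
| Day 169 (dosed on site at Visit 6) | 169 − 1 + 1 = 169 | 197 | 28 days; 28/169 = 16.6% |

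Both rows are shown because Protocol 5.2 has drug given on site on visit days, so a Day 169 dose cannot be excluded.

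**Visit windows.** If follow-up is timed from the last treatment, as SAP 2.2.1 words it, the gap stays at about 28 days. If the two windows vary independently around their nominal days, Visit 6 falls on Day 162 to 176 and Visit 7 on Day 190 to 204. The gap between visits then runs from 190 − 176 = 14 to 204 − 162 = 42 days. A last dose on the day before Visit 6 makes it 15 to 43. The overall range is 14 to 43 days.

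**Effect on an arm mean, per affected patient.**
- Placebo (n=3): 28/3 = 9.3 to 29/3 = 9.7 days.
- Either dose arm (n=6): 28/6 = 4.7 to 29/6 = 4.8 days.

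**Early stopper who stays in follow-up.** Protocol 4.4 and 4.6 keep such patients under observation, so the last visit can fall well after the last dose. As an illustration only, a patient whose last dose was on Day 60, unrecorded, and who attended on Day 197 would gain 197 − 60 = 137 days.

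**Patient lost while on drug.** Loss to follow-up is a listed reason for discontinuation (Protocol 4.5). The last visit is then an on-treatment visit. A patient lost after Visit 4 (Day 85) leaves with 42 + 7 = 49 tablets and could go on dosing for about seven weeks. Here the rule is accurate or understates exposure.

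**The case against.** The strongest reply is that this is a rarely used fallback with a narrow reach. The documents provide several chances to obtain the date: compliance checks at Visits 3 to 6, drug-accountability logs (Protocol 5.3 and 9.2.1), queries on missing data (Protocol 9.2.2.5; SAP 6.8), and a study completion form for discontinued patients (Protocol 4.5). No expected frequency of missing last-dose dates is given. All of this stands, and it limits the importance of the point. It does not change what the rule yields when it is used.

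The SAP also never formally defines the last visit. If it meant the last visit on treatment, the problem would disappear. That reading gives one term two meanings within a paragraph, so it cannot be assumed.

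A reader might infer three stronger things that the documents do not support:

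- *That exposure is overstated for everyone to whom the rule applies.* It is not: for a patient lost while on drug the error is nil or in the other direction. Nor do the documents show which kind of patient is more likely to lack the date.
- *That compliance and membership of the per-protocol set are distorted.* The compliance denominator in SAP 7.3.1 is the "expected number of tablets to be taken during the study period". It is not derived from treatment duration or from the substituted date, so this consequence needs a link that the SAP does not make.
- *That adverse-event counts or efficacy results change.* The treatment-emergent period in SAP 7.3.2 runs until the patient exits the study, and no efficacy endpoint uses treatment duration.

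**Conclusion.** The rule is wrong as written for any patient with no recorded last-dose date who attends a visit after stopping drug. For a completer who attends Week 28, the excess is 28 to 29 days (about 17%) at nominal visit days, and 14 to 43 days if the windows vary independently. An early stopper who stays in follow-up can have a larger error.

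This rests on reading the last visit as the study-exit visit and on a first dose on Day 1. The total effect cannot be sized, because the number of missing dates is not given. It is confined to the descriptive treatment-duration summary. Severity: minor.

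**What to change.** Replace the last-dose fallback in SAP 7.3.1 with wording such as:

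> Where the last-dose date is missing, the earlier of the following will be used: (a) the date of the Week 24 or End-of-treatment visit, or of the last attended visit before it if that visit was not attended; (b) the last dosing date supported by drug-accountability records. A post-treatment follow-up visit will not be used.

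Part (a) alone is sufficient for completers: the nominal duration becomes 169 days, against 168 or 169 actual. It is not sufficient for early stoppers. In the Day 60 illustration, a patient who attended Week 24 would still be overstated by 169 − 60 = 109 days, which is why part (b) is needed. Where accountability records are also silent, some error will remain, and the CSR should flag imputed durations.

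The cost is a short SAP revision and a small change to the exposure program. The accountability records are already required by the protocol, so no new data are needed.
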